Milestone 3: We will calculate the association between frequency of cannabis use (days) and total quantity of cannabis consumed per week based on participants' EMA data concerning quantity of cannabis use.

If the proposed R21 milestones are met, we will complete the following specific aims during the R33 phase:

R33 Aim 1: Assess the impact of reduced frequency and quantity of cannabis use on functioning.

Hypothesis 1a: Decreased cannabis use will be associated with significant improvements in mental health symptoms, self-efficacy, physical activity, and health-related quality of life.

Hypothesis 1b: Decreased cannabis use will be associated with significant improvements in working memory, impulsivity, and drugged driving.

R33 Supplementary Aim: Explore momentary (e.g., craving, sleep) and between-person factors (e.g., sex, baseline use) that might moderate the association between cannabis use and functioning.

Expected Outcomes: The proposed research will be the first study to systematically assess the impact of reduced frequency and quantity of cannabis use on functioning. As such, these findings will directly inform ongoing efforts to include reductions in illicit drug use as a valid, clinically-meaningful outcome measure in clinical trials of pharmacotherapies for the treatment of CUD and other substance use disorders (Tiffany et al., 2011; Donovan et al., 2011).

A. SIGNIFICANCE

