to stress, trauma, and coping strategies. Participants will be informed about these new study procedures verbally, and the study team member who informs them will provide a note-to-fil indicating so. Participants can refuse to complete these measures. We will ask ongoing participants to complete these measures at their next study visit or follow-up session. When study enrollment begins again, participants will complete these measures at the screening session. We are adding the CAIR Pandemic Impact Questionnaire (Lang, 2020; https://www.nlm.nih.gov/dr2/CAIR-PIQ_scoring.pdf), and another measure, COVID Core Questions, with variables of interest. If a participant endorses any item marked with an asterisk on the COVID Core Questions measure, we will ask them to complete a PTSD Checklist 5 related to that specific event. Finally, we have added a measure designed to evaluate participants' satisfaction with remote study procedures.

E. DATA ANALYSIS PLAN

Multilevel modeling (MLM) will be used to analyze the EMA data. MLM is a technique for analyzing repeated observations of data across multiple individuals. Unlike repeated-measures ANOVA, MLM can incorporate time-varying (Level-1) and time-invariant (Level-2) predictors. MLM can also accommodate imbalanced data and unequal variances. The main conclusions drawn from this study will be based on the pre-specified hypotheses, which will be tested with two-sided statistical tests at an alpha of .05. Analyses will be performed with SAS for Windows (Version 9: SAS Institute, Cary, NC).

E.1. Missing Data.

Although we do not anticipate much missing baseline data, we do anticipate missing values in the EMA data. MLM procedures, which will be used to analyze H_{1A}, H_{1B}, and the supplementary aim, are based on maximum likelihood estimation and use all available data. As such, MLM can accommodate data missing at random. Missing data will be examined to determine whether missingness is random or systematically associated with baseline variables. Those baseline parameters associated with missingness will be covaried. If data are suspected to be missing not at random (i.e., only certain values are likely to be missing), multiple imputation will be used to analyze non-random patterns of missing EMA data (Schafer & Graham, 2002).

E.2. Electronic Diary Compliance and EMA Data Reduction.

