During the 8-week EMA data collection, we will calculate the percentage of responses recorded within 5 minutes of the random prompts. We will exclude responses delayed by longer than 5 minutes from the analyses. Data will be aggregated at the day-to-day level to indicate the following: whether cannabis was used; the total number of joints/grams consumed; mean daily potency; mean daily levels of mental health symptoms, self-efficacy, health-related quality of life, working memory, and impulsivity; whether participants drove while intoxicated; and total amount of physical activity. By using multi-daily records to examine day-level phenomena, we will minimize measurement error related to poor recall and random variability. For the 2-week baseline period and each week of the 6-week experimental period, we will calculate frequency of cannabis use as the number of days used per week. To quantify change in frequency of cannabis use from baseline, change scores will be calculated by subtracting number of days per week of cannabis use during the 2-week baseline from those levels

recorded during each week of the mCM treatment period. A dichotomous variable will also be calculated reflecting whether a given participant achieved at least a 50% reduction in cannabis use during a given week. Thus, the data will be structured such that each participant will have up to 56 rows of data corresponding to each day of the 2-week baseline period and 6-week mCM/non-contingent control. Each row will contain a dichotomous indicator of whether or not cannabis was consumed that day, total quantity of cannabis consumed that day, total THC load of the cannabis used that day, daily estimates of functioning, a baseline estimate of cannabis use, and three variables capturing weekly varying frequency, quantity, and total THC load of cannabis use: the aforementioned dichotomous variable measuring whether a 50% reduction from baseline use was achieved and a change score, with a 0 change-score value for days falling during the 2-week baseline.

E.3. Hypotheses 1a and 1b.

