To examine the effect of reduced cannabis use on functioning assessed with EMA, day-by-day outcome variables will be modeled *via* MLM as a function of treatment group (Level 2), week (Level 1; with the two baseline weeks treated as a single week), and treatment-by-week interactions. Daily consumption (total equivalent number of joints/gram consumed and total potency; Level 1) will be examined as potential covariates. Linear and quadratic time effects will be explored. Week-by-week effects of cannabis reduction will be examined in separate models. We will also examine the effects of reduced use by modeling day-by-day and week-by-week outcomes as a function of week-by-week reductions in cannabis, independent of treatment group. Linear MLM will be used to model normally distributed outcome variables *via* PROC MIXED. Generalized linear MLM will be used to model dichotomous and otherwise non-normally distributed outcome variables *via* PROC GLIMMIX.

E.4. Supplementary Aim.

To examine whether reduced cannabis use moderates or is moderated by other factors (e.g., sex differences), the models examined in Hypotheses 1a and 1b will be modified to include potential Level-1 (e.g., day-to-day craving, sleep) and Level-2 (e.g., sex, baseline cannabis use, self-efficacy) predictors as well as their interactions with week-by-week change in cannabis use. For instance, to determine whether a week-by-week reduction in cannabis use moderates the association of day-by-day cannabis use (or abstinence) with daily working memory, whether or not participants used cannabis that day (Level 1) will be added as a predictor of working memory as will its interaction with week-by-week change in frequency or quantity of cannabis use. This particular model could thus determine whether cannabis users demonstrate greater cognitive functioning on abstinent days when they reduce their cannabis use.

E.5. Power Calculations.

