Power calculations are based on Hypotheses 1a and 1b and were performed with Power Analysis and Sample Size software (PASS, Version 12: NCSS LLC, Kaysville, Utah). We conservatively estimate that as many as 12 participants could potentially need to be excluded due to sustained abstinence, leaving a minimum of 60 participants available for analysis. The corresponding analyses make use of multilevel data with a total sample of up to 3,360 records (60 participants X 56 daily observations). Because there will only be 7 unique estimates per participant of week-to week change in frequency of cannabis use, a conservative minimum estimate of the effective sample size is 420 (60 participants X 7 weekly

observations). Although these observations are non-independent given clustering within participants, hence the use of MLM, accounting for variation between participants will reduce the error variance in the dependent variables. Thus, the effective sample size will very likely exceed 420. An effective sample size of 420 has 90% power to detect small-to-medium treatment effects equivalent to Cohen's $d = 0.30$ or associations equivalent to $r = .16$.

References

Adkisson, K., Cunningham, K.C., Dedert, E.A., Dennis, M.F., Calhoun, P.S., Elbogen, E.B., Beckham, J.C., & Kimbrel, N.A. (manuscript under review). Cannabis use disorder and post-deployment suicide attempts in Iraq/Afghanistan-era veterans.

Babor TF, de la Fuente JR, et al., 1989. AUDIT The Alcohol Use Disorders Identification Test: Guidelines for use in primary health care (WHO/MNH/DAT 89.4). Geneva, Switzerland.

Beckham, J.C., Adkisson, K.A., Hertzberg, J., Kimbrel, N.A., Budney, A.J., Stephens, R.S., Moore, S.D., & Calhoun, P.S. (manuscript under review). Mobile contingency management as an adjunctive treatment for co-morbid cannabis use disorder and cigarette smoking.

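### E.5 gives one power figure, in Cohen's d and r, for all of Hypotheses 1a and 1b, but states no event rate, odds ratio or power for drugged driving, a daily yes/no outcome analysed with PROC GLIMMIX

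*Combined protocol and SAP*

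**What the plan says.** Hypothesis 1b (Specific Aims, R33 Aim 1) reads "Decreased cannabis use will be associated with significant improvements in working memory, impulsivity, and drugged driving". Section E.2 reduces the diary data to day level, and for driving the day-level variable is "whether participants drove while intoxicated". Section E.3 assigns the model by outcome type: linear MLM in PROC MIXED for normally distributed outcomes, while "Generalized linear MLM will be used to model dichotomous and otherwise non-normally distributed outcome variables" in PROC GLIMMIX. The opening of section E says the hypotheses will be "tested with two-sided statistical tests at an alpha of .05".

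Section E.5 opens with "Power calculations are based on Hypotheses 1a and 1b". It takes 60 analysable participants and 7 weekly values each, says that "a conservative minimum estimate of the effective sample size is 420", adds that the real figure will very likely be larger, and concludes that "An effective sample size of 420 has 90% power to detect small-to-medium treatment effects equivalent to" d = 0.30, or an association of r = .16. It does not say what equivalence to d means for a yes/no outcome.

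**The concern.** A standardised mean difference or a correlation is enough to fix power for a continuous outcome once N and alpha are set. For a yes/no outcome on the log-odds scale it is not: the information per observation depends on the event rate, and falls as the event becomes rare. E.5 names H1b without exception, so a reader will take the 90% to cover drugged driving.

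The Specific Aims present drugged driving and traffic accidents as a main harm of heavy use, and D.1 describes the R33 phase as fully powered. If the daily rate is low, a non-significant result on this outcome could be read as evidence of no effect from a well-powered test, when the plan contains nothing to support that reading.

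**Working it through.** **Inputs.** Two-sided alpha .05 (section E). Effective N = 60 × 7 = 420, d = 0.30, r = .16 and power 90% (E.5). Allocation 2:1, 48 to 24 (D.1). Splitting 420 in that ratio gives 280:140. Excluding up to 12 sustained abstainers could move the ratio towards 36:24 if all were in the Reduced Use arm, so 2:1 and 1:1 (210:210) are both shown. The drugged-driving rate is not in the documents; every rate below is an assumption.

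**Step 1: the plan's own figure, continuous outcome.** Power = Φ(d × √[n₁n₂/(n₁+n₂)] − 1.960).

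- 1:1: 0.30 × √105 = 3.074; 3.074 − 1.960 = 1.114; power 86.7%.
- 2:1: 0.30 × √93.33 = 2.898; 2.898 − 1.960 = 0.938; power 82.6% (82.4% with the noncentral t).
- Detectable d at 90%: 0.316 (1:1) or 0.336 (2:1).
- For r = .16: Φ(0.1614 × √417 − 1.960) = 90.9%. This half reproduces, but r = .16 corresponds to d = 2 × .16/√(1 − .0256) = 0.32, not 0.30.

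So d = 0.30 does not reach 90% at N = 420 under the planned two-sided test, even for a continuous outcome. The comparator for the binary case is 82.6% or 86.7%.

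**Step 2: d = 0.30 on the logit scale.** ln OR = d × π/√3 = 0.30 × 1.8138 = 0.544, so OR = 1.72. Treated odds = control odds / 1.72.

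**Step 3: power at N = 420.** With p̄ the overall rate,
power = Φ{ [|p₁−p₂| − 1.960 √(p̄(1−p̄)(1/n₁+1/n₂))] / √(p₁(1−p₁)/n₁ + p₂(1−p₂)/n₂) }.

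Worked case, control rate 10%, 140 control and 280 treated: p₂ = .0606; p̄ = .0737; numerator .0394 − 1.960 × .02705 = −.0136; denominator .0291; Φ(−0.468) = 32%.

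| Control rate (assumed) | Treated rate | Power 2:1 | Power 1:1 | Total N for 90%, 2:1 | Total N for 90%, 1:1 |
|---|---|---|---|---|---|
| 50% | 36.7% | 74.0% | 78.6% | 654 | 582 |
| 30% | 19.9% | 63.0% | 66.6% | 858 | 772 |
| 20% | 12.7% | 50.6% | 52.9% | 1,182 | 1,066 |
| 10% | 6.1% | 32.0% | 31.8% | 2,205 | 1,994 |
| 5% | 3.0% | 20.1% | 18.6% | 4,275 | 3,874 |

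The maximum over control rates is 74.6% (2:1) or 79.3% (1:1), at a control rate of about 56–57%.

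**Step 4: loss due to the binary outcome, like for like.** Best case: 82.6 − 74.6 = 8.0 points (2:1); 86.7 − 79.3 = 7.4 points (1:1). At a 10% rate: 82.6 − 32.0 = 50.6 points; 86.7 − 31.8 = 54.9 points.

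**Step 5: other readings of equivalence to d.** A probit shift of 0.30 gives at most 63.7% (2:1) or 68.7% (1:1), and about 38% at a 10% rate. Cohen's h = 0.30 gives about 79–87% over control rates of 5% to 60%. It then implies 50% falling to 35.2% (OR = 1/(.3522/.6478) = 1.84), or 10% falling to 2.9% (OR = .1111/.0301 = 3.7). None of the three reaches 90% at N = 420.

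**Step 6: sensitivity to effective N (logit reading, 10% rate; 2:1 / 1:1).** N = 840: 53.8% / 55.7%. N = 1,260: 70.0% / 73.1%. N = 3,360: 97.8% / 98.8%. In the other direction, for a purely between-person contrast over 56 days the design effect is 1 + 55 × ICC. The 3,360 daily records fall below 420 effective ones once ICC exceeds (3,360/420 − 1)/55 = 0.127; at an assumed ICC of 0.3 they are worth 3,360/17.5 = 192.

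**The case against.** The strongest reply is that the percentages above rest on choices the documents do not make. E.5 says only that effects are equivalent to d, so the logit conversion is the reviewer's. With Cohen's h the continuous power is roughly kept, and near a 50% rate the implied odds ratio of 1.84 is not far from 1.72. That stands: a reader might infer that power for drugged driving can never exceed 75–80%, and the documents do not support this as a general ceiling. It holds only for OR 1.72 at N = 420. What limits the h reading is that at low rates it describes a large effect (OR 3.7 at 10%).

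The two-proportion approximation is also not the planned model. It treats each of 420 participant-weeks as one yes/no observation, whereas each week holds up to 7 daily records, the model includes the ad lib baseline, and the plan calls 420 a minimum. This stands too, but it cuts both ways: treatment is a Level 2 factor, and clustering can push the effective N below 420. No within-person correlation is given, so the direction cannot be settled.

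Finally, a reader might infer that power is about 30%, or that the whole gap from 90% comes from the binary outcome. Neither follows. The 10% rate is an assumption with no support in the documents over 30% or 50%, and part of the gap is E.5's separate shortfall at d = 0.30 for a continuous outcome. Nor does E.5 show that a mean-difference formula was run on drugged driving; it names the software but no formula for any outcome.

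**Conclusion.** The point holds as a gap in the power statement. E.5 claims coverage of all of H1b, and for its one dichotomous outcome the documents supply none of what a power figure needs: event rate, odds ratio, within-person correlation or a binary calculation. At the plan's own N of 420 and two-sided .05, none of the three readings of d = 0.30 examined gives 90%.

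The size is conditional. Reading d = 0.30 as OR 1.72, power is about 74–79% at a 50% control rate, 63–67% at 30%, 51–53% at 20% and 32% at 10%. The part attributable to the yes/no outcome is about 8 points at best and a little over 50 points at a 10% rate. These figures assume the event rates, the logit conversion and 420 independent yes/no observations. The supportable conclusion is that the 90% is unsupported for drugged driving, not that its true power is any particular number. The linear-MLM outcomes in H1a and H1b are not affected by this point.

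**What to change.** In E.5, limit the d = 0.30 / r = .16 statement to outcomes modelled by linear MLM. Add one or two sentences for drugged driving giving either the power for OR 1.72 or the detectable odds ratio in the GLIMMIX model, with the assumed daily rate, within-person correlation and effective N, each over a range. The R21 ad lib EMA data can inform the rate and correlation, since C.6 says all EMA procedures are piloted in that phase. With a planned 18 participants and 14 ad lib days each the estimates will be imprecise, which is why a range is needed. If power turns out low, say in advance that the drugged-driving part of H1b will be reported as an estimate with a confidence interval and not as a 90%-powered test.

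The cost is a short calculation and a less favourable stated power for one outcome. No change to design, sample size or data collection is needed.
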